11.4 Procedures for Reporting Pregnancy

A positive urine pregnancy test or any hCG level ≥ 5 IU/L for females of child-bearing potential and ≥ 8 IU/L for post-menopausal females will be assessed as clinically significant and will result in the immediate dismissal of the subject from the study, unless deemed otherwise by the Investigator. The elevated hCG will be investigated as a potential pregnancy and will be followed up in the same manner as an AE. A confirmatory hCG blood test will be required for any elevated values. If pregnancy is confirmed, any out of range hCG levels will not be considered an adverse event.

Once notified that pregnancy has occurred during the course of the study or within 30 days of study completion, clinic personnel will report the pregnancy within 24 hours of the confirmatory hCG blood test, to the PI/Sub-Investigator, the IRB, and appropriate Sponsor representative. A Pregnancy Notification Form will be completed as per BPSUSA internal Standard Operating Procedures and will be included alongside any pertinent information at the time of pregnancy reporting. The confirmed pregnancy will be followed to birth of the child or elective/spontaneous termination of the pregnancy. Follow up will occur at minimum once every three months (i.e., once per trimester) until the end of the pregnancy (birth, termination, etc.).

Elective termination will not be considered an adverse event, however supporting documentation detailing the outcome of the procedure will be required. Spontaneous

termination of the pregnancy will be considered a Serious Adverse Event and will be followed up accordingly (as per [Section 11.3](#)). Pregnancy will be treated as AEs for this study.

12.0 BIOANALYTICAL ANALYSIS

12.1 Analytical Procedures

Data management, quality review and reporting of study data pertaining to laboratory analysis of study data will be the responsibility of the bioanalytical facility.

12.1.1 Samples to be Assayed

Sample from all subjects who complete at least 1 study period will be analyzed for drug concentration.

12.1.2 Analyte(s) in Biological Matrix

Whole blood samples will be assayed for tacrolimus using a validated analytical method according to the principles of Good Laboratory Practice.

12.1.3 Incurred sample reproducibility

Incurred Sample Reanalysis (ISR) shows repeatability and stability of an analytical method in real sample matrix. Approximately 10% of the samples will be reanalyzed in case the number of samples is less than 1000 samples. If the number of samples is greater than 1000, 10% of the first 1000 samples and 5% of the remaining samples will be reanalyzed. The ISR test will contain samples from all analyzed subjects. For each subject, at least two samples should be chosen, one at or near C_{max} and the other one in the elimination phase.

If an ISR sample result is not valid for analytical reasons (e.g. low area of internal standard response, sample processing error, instrument failure etc.), this sample will be excluded from the statistical evaluation of the ISR test and will not be reanalyzed. Acceptance criterion of the ISR test: the concentration obtained for the initial analysis and the concentration obtained by reanalysis should be within 20% of their mean for at least 67% of the repeats. If acceptance criterion of the ISR test is not met, an investigation will be conducted to determine the reason for differences, and adequate steps will be taken to minimize inaccuracy (and imprecision).

The ISR test results will be presented in the Bioanalytical Report; they will not be used for any correction of the concentration results for pharmacokinetic and statistical evaluation of the study.

13.0 PHARMACOKINETIC AND STATISTICAL ANALYSIS

13.1 Pharmacokinetic and Statistical Analysis Data Set

The data from at least one of the following subjects will be included in the PK and statistical analysis:

1. Subjects who complete all study periods.
2. Subjects who have missed samples but for whom it has been predicted prior to the start of bioanalytical analysis that reliable estimates of the PK parameters should be possible.
3. Subjects who drop out from the study but have completed at least 2 periods.

If a subject's pre-dose concentration is less than or equal to 5% of the C_{max} value for that subject in the given period, then the subject's data in that period without any adjustments can be included in all PK measurements and calculations. If the pre-dose value is greater than 5% of the C_{max} , data from that subject in that period will be dropped from the PK and statistical analysis. Data for subjects dropped due to higher than 5% of C_{max} pre-dose concentrations will be included in a separate appendix in the final study report.

For subjects who are dismissed from the study due to non-compliance or any reason other than AEs, other data of non-impacted period(s) for that subject, which fulfills the PK analysis data set requirements, as above, will be included in PK stats analysis. Data does not fulfill the requirements will be presented separately.

If a subject is dismissed/withdrawn due to an AE from a study period, the data from that period will not be included in the PK stats analysis and will be presented separately. All other data for that subject, which fulfills the PK analysis data set requirement, as above, will be included in PK stats analysis. Data does not fulfill the requirements will be presented separately.

Data from other subjects who were dismissed or withdrew due to elevated hCG levels or are confirmed to be pregnant will not be included in the PK and statistical analysis. The data for these subjects will be presented separately.

Any decision for excluding data prior to start of sample bioanalysis (e.g Major protocol deviation) will be provided with a detailed explanation and will be properly recorded and dated.

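### Section 13.1 excludes the whole subject for raised hCG or pregnancy without giving a reason, while the neighbouring dismissal rules keep unaffected periods (minor, cheap to fix)

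*Combined protocol and SAP*

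**What the plan says.** Section 13.1 defines the analysis data set and then gives three dismissal rules.

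- **Dismissal for an AE.** "If a subject is dismissed/withdrawn due to an AE from a study period, the data from that period will not be included". The rule then keeps the rest: "All other data for that subject, which fulfills the PK analysis data set requirement, as above, will be included in PK stats analysis".
- **Dismissal for any other reason.** For subjects "dismissed from the study due to non-compliance or any reason other than AEs, other data of non-impacted period(s) for that subject" is kept if it meets the same requirements.
- **Raised hCG or pregnancy.** "Data from other subjects who were dismissed or withdrew due to elevated hCG levels or are confirmed to be pregnant will not be included". These data are presented separately. Nothing is said about which period, when the test turned positive, or why.

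The requirements that the first two rules refer to include rule 3 of the data set: "Subjects who drop out from the study but have completed at least 2 periods".

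Section 11.4 bears on how the event is classed. It says "Pregnancy will be treated as AEs for this study", but also that a raised hCG "will be investigated as a potential pregnancy and will be followed up in the same manner as an AE", and that "If pregnancy is confirmed, any out of range hCG levels will not be considered an adverse event".

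On timing, Section 2.0 and Appendix A schedule a serum test at screening and a urine test at each period check-in, before dosing. No test is scheduled at end of study. Section 5.1.2.1 dismisses a subject at once on a positive urine hCG, whereas Section 11.4 leaves room for the investigator to decide otherwise. Section 11.4 also covers pregnancies notified within 30 days of study completion.

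**The concern.** The hCG sentence is stricter than both rules beside it, so the difference does not depend on how the event is classed. If pregnancy is handled as an AE, the AE rule would keep her other qualifying periods. If a raised hCG is not an AE, the rule for other reasons would keep her unaffected periods.

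Three groups are affected:

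- A woman positive at Period 3 or Period 4 check-in has no PK data in the period of detection. All that the sentence removes is earlier periods, each entered on a negative test.
- A woman dismissed on a raised hCG that the confirmatory blood test does not bear out is still excluded entirely, because dismissal for the raised level is enough.
- Read literally, a woman who completes all four periods and is confirmed pregnant after her last sample loses all four.

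At stake are usable Cmax and AUC72 values. Sections 7.1 and 7.6 do not replace dosed subjects, and Section 13.2.2 needs both reference administrations for S_WR.

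**Working it through.** **The plan's own figures.** Section 7.1 gives 64 + 8 = 72 enrolled and at least 48 completers. The step from 64 to 48 implies an allowance of (64 − 48)/64 = 25%. No power, within-subject SD, assumed ratio or dropout rate is stated, so no power figure can be reproduced.

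**What each subject could supply.** Inputs are the sequences TRTR and RTRT (Section 5.3), 28 samples per period (Section 8.9), the two-period minimum (Section 13.1, rule 3), and the definitions in Section 13.2.2. There, I_ij needs all four periods and D_ij needs both periods on one product. The table shows what a period-level rule would keep and the present sentence removes, assuming that no earlier period overlaps the pregnancy.

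| Positive test | Periods removed from analysis | Samples | D_ij | I_ij |
|---|---|---|---|---|
| Period 2 check-in | 0 extra (1 period fails the minimum) | 0 | none | none |
| Period 3 check-in | 2 (one T, one R) | 28 × 2 = 56 | none | none |
| Period 4 check-in | 3 (TRT or RTR) | 28 × 3 = 84 | one: T pair in TRTR, R pair in RTRT | none |
| Confirmed after Period 4 | up to 4 | up to 28 × 4 = 112 | both | one |

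So a dismissal at check-in never touches the scaled point estimate. Only a Period 4 dismissal touches a within-subject variance, and then for one product.

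**Effect on the unscaled T − R standard error.** Assume equal within-subject variance s² for both products and no subject-by-formulation variance, and ignore the period adjustment. The variance of one subject's T − R is s²/2 + s²/2 = s² with four periods, s²/2 + s² = 1.5s² with three, and s² + s² = 2s² with two. A subject is therefore worth w = 1, 2/3 or 1/2 of a full subject. With 48 subjects of whom k are affected, dropping them instead of keeping their periods multiplies the SE by √[(48 − k + kw)/(48 − k)].

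| k | 2 periods | 3 periods | 4 periods |
|---|---|---|---|
| 1 | √(47.5/47): +0.53% | √(47.667/47): +0.71% | √(48/47): +1.06% |
| 2 | √(47/46): +1.08% | √(47.333/46): +1.44% | √(48/46): +2.15% |
| 4 | √(46/44): +2.25% | √(46.667/44): +2.99% | √(48/44): +4.45% |

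A generalised least squares calculation for the mixed model agrees to within 0.05 of a percentage point for s between 0.10 and 0.30. Against 64 subjects, one affected subject adds 0.40%, 0.53% or 0.79%.

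**Effect on power.** The three criteria of Section 13.4 were simulated together, with whole four-period subjects removed as an upper bound. The SD (0.10 to 0.30) and the true ratio (0.95 to 1.00) are assumptions. In the least favourable case tried (SD 0.10, ratio 0.95), joint power was 92.0% at 48 subjects, 91.8% at 47, 91.1% at 46 and 90.3% at 44. In every other case the fall from 48 to 44 was under 1 percentage point.

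**The case against.** The best defence is that the sentence is a deliberate, conservative carve-out. It is written as a separate category, is unconditional, and depends neither on treatment nor on concentrations. A specific rule of that kind governs over the general ones. This stands, and it rules out a stronger reading that a reader might infer: that Sections 13.1 and 11.4 give the same woman two conflicting dispositions, to be chosen between once concentrations are known. Section 11.4 is about reporting and follow-up, not analysis sets, and it does not class a raised hCG as an AE once pregnancy is confirmed. The difficulty is an unexplained difference in strictness, not an open choice.

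A reader might also infer that the data are lost. They are not: Section 12.1.1 assays every subject who completes at least one period, and Section 13.1 presents the excluded data separately. They leave only the inferential analysis.

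Nor may every earlier period be taken as valid. The objective concerns non-pregnant women, dosing may be only 14 days apart, and the documents give no sensitivity for the urine test. Period 3 may overlap a pregnancy found at Period 4 check-in, so three recoverable periods is a best case.

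Finally, the investigator's discretion in Section 11.4 may keep some unconfirmed rises from ending in dismissal. That helps only in part, because Section 5.1.2.1 states immediate dismissal; the two sections need to be reconciled. Section 13.2.2 defers further detail to the SAP, but nothing more on this rule appears in the text reviewed.

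**Conclusion.** The point holds as a minor, cheap improvement. Whole-subject exclusion is stricter than both neighbouring rules and no reason is given. It also reaches two groups whose data the documents give no ground to doubt: subjects whose raised hCG is not confirmed as pregnancy, and completers who conceive after the last sample.

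The size is about 0.5% to 1.1% on the T − R standard error per affected subject against 48, with little change in power. This rests on the assumed variance structure and on the earlier periods being usable. How many subjects would be affected cannot be said: the documents give neither the share of women nor an event rate, and Section 7.2 requires contraception for women who can conceive.

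That the exclusion falls only on women might suggest bias. The documents do not support this. The comparison is within subject and the rule is blind to formulation, so no distortion of T against R is evident.

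**What to change.** Replace the hCG sentence in Section 13.1, and its counterpart in the SAP, with a period-level rule:

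- Exclude the period in which pregnancy is detected and any earlier period that may overlap it. The decision is made and dated before bioanalysis, without reference to concentrations.
- Include all other periods that meet the data-set requirements.
- If the confirmatory test excludes pregnancy, include all completed periods that meet those requirements.
- State that a pregnancy arising after the last sample does not remove completed periods.

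Reconcile the wording with Section 11.4, so that the status of pregnancy and of raised hCG is the same in both places. If whole-subject exclusion is intended after all, give the reason in Section 13.1.

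The cost is a few lines of text and no extra sampling. The downside is a documented judgement on overlap, which the present rule avoids and for which Section 11.4 sets out no dating procedure.

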13.2 Analysis of Pharmacokinetic Data

The PK and statistical analysis will be performed at BPSI using SAS[®] Version 9.4.

The PK and/or statistical analyses outlined in this protocol may be altered with appropriate justification.

13.2.1 Pharmacokinetic Analysis

Pharmacokinetic parameters will be calculated using non-compartmental analysis (NCA) method. The following PK parameters will be estimated (where possible) for tacrolimus and included in the PK and statistical analysis:

Primary endpoint

AUC_{72} :	Area under the concentration-time curve from time zero until time point 72 hours post dose. AUC_{72} is estimated using the linear trapezoidal method.
C_{max} :	The maximal observed whole blood concentration.

Secondary endpoint

AUC_{inf} :	Area under the concentration-time curve from time zero to infinity, calculated as $AUC_t + C_{last}/\lambda$, where C_{last} is the last measurable concentration.
AUC_t :	Area under the concentration-time curve from time zero until the last measurable concentration or last sampling time t, whichever occurs first. AUC_t is estimated using the linear trapezoidal method.
$T_{1/2}$:	Terminal elimination half-life, estimated as $\ln(2)/\lambda$.
T_{max} :	Time when the maximal whole blood concentration is observed.
λ :	Terminal elimination rate constant, estimated by linear regression analysis of the terminal portion of the ln-concentration vs. time plot.

During PK and statistical analyses, drug concentrations below the lower limit of quantitation (BLQ) of an assay will be considered as zero except when they occur between two non-BLQ concentrations where they will be considered as missing during PK calculations and estimations.

The actual time of blood samples collection will be used for pharmacokinetic and statistical analysis.

Missed samples and non-reportable concentrations (e.g. quantity not sufficient) from the analytical laboratory will be treated in the pharmacokinetic analysis as if they have not been scheduled for collection.

For subjects with missing or non-reportable tacrolimus concentration at time point 72-hour or the sampling time deviation at 72-hours is greater than 2 hours, the AUC_{72} will not be calculated. If concentration(s) at 72 hours or at the time point(s) immediately preceding 72 hours is/are BLQ(s), this/these BLQ value(s) will be set as zero and the calculated AUC will be treated as AUC_{72} .

The λ , $T_{1/2}$, and AUC_{inf} parameters will not be estimated for whole blood concentration-time profiles where the terminal linear phase is not clearly defined.

For subjects with missing or non-reportable tacrolimus concentrations for three or more of the last samples, only the C_{max} and T_{max} will be presented and included in the statistical analysis. Other PK parameters will not be reported. The AUC_{72} could also be estimated for these subjects if data allows.

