13.2.2 Statistical Analysis of Pharmacokinetic Data

Step 1: Determine the Within-subject Standard Deviation of the Test and Reference Products (S_{WT} and S_{WR}) for the PK Parameters AUC_{72} , AUC_t , AUC_{inf} and C_{max} :

The within-subject standard deviation of the test and reference products will be determined for the ln-transformed PK parameters AUC_{72} , AUC_t , AUC_{inf} and C_{max} for tacrolimus.

For a fully replicated 4-way design with 2 sequences TRTR, RTRT, the within subject variance of the reference product, S_{WR}^2 can be determined as follows:

$$S_{WR}^2 = \frac{\sum_{i=1}^2 \sum_{j=1}^{n_i} (D_{ij} - \bar{D}_i)^2}{2(n-2)}$$

Where,

i = Number of sequences (2 used in the study),

j = Number of subjects within each sequence,

$D_{ij} = R_{ij1} - R_{ij2}$ (where R_{ij1} represents the first administered (early) reference and R_{ij2} represents the second administered (late) reference.)

$$\bar{D}_i = \frac{\sum_{j=1}^{n_i} D_{ij}}{n_i} \text{ (Mean within sequence } i \text{.)}$$

$n = \sum_{i=1}^2 n_i$ (total number of subjects used in the study, while n_i is the number of subjects used in sequence i .)

S_{WR} will be calculated as follows:

$$S_{WR} = \sqrt{S_{WR}^2}$$

The S_{WR} calculation will include subjects with estimated PK parameters for both reference administrations.

For a fully replicated 4-way design with 2 sequences TRTR, RTRT, the above method can be applied for the calculation of the within subject variance of the test product S_{WT} as well.

Step 2: Reference Scaled Average Bioequivalence Procedure

The 95% upper confidence bound for $(\mu_T - \mu_R)^2 - \theta S_{WR}^2$ will be determined for the ln-transformed PK parameters AUC_{72} , AUC_t , AUC_{inf} and C_{max} using a PROC MIXED model in SAS[®], where μ_T and μ_R are the means of the ln-transformed PK parameters obtained from the BE study for the test and reference products, respectively. θ is the scaled average bioequivalence limit defined as $\theta = \left(\frac{\ln(1/0.9)}{\sigma_{w0}}\right)^2$, where σ_{w0} is a regulatory constant which is set at 0.10.

The method of obtaining the upper confidence bound is based on *Howe's Approximation* [8]. The following steps will be followed to construct the 95% upper confidence bound.

- Let T_{ij1} , T_{ij2} , R_{ij1} and R_{ij2} be the log transformed observations on early test, late test, early reference and late reference for subject j within sequence i . Then we will calculate the following two terms:

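### Cmax has no evaluability rule: a profile cut off before its peak still enters the primary analysis, and one such reference value can loosen the scaled limit

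*Combined protocol and SAP*

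**What the plan says.** Section 13.2.1 defines Cmax, a primary endpoint, as "The maximal observed whole blood concentration". Missed and "non-reportable concentrations (e.g. quantity not sufficient) from the analytical laboratory will be treated in the pharmacokinetic analysis as if they have not been scheduled". The section ends with a rule for truncated profiles: with missing or non-reportable results for "three or more of the last samples, only the C_{max} and T_{max} will be presented and included in the statistical analysis". It sets no limit on how early sampling may have stopped.

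Other parameters do have adequacy rules there. AUC72 is not calculated if the 72 h result is missing or non-reportable, or if "the sampling time deviation at 72-hours is greater than 2 hours". Lambda, T1/2 and AUCinf need a defined terminal phase.

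Section 13.1 sets entry to the analysis: "The data from at least one of the following subjects will be included in the PK and statistical analysis". The three routes are completing all periods, having missed samples but with reliable estimates predicted before bioanalysis, and "Subjects who drop out from the study but have completed at least 2 periods". It also removes a period ended by an AE and lets other exclusions be recorded before bioanalysis.

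In section 13.2.2, Step 1, the S_WR "calculation will include subjects with estimated PK parameters for both reference administrations".

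**The concern.** An observed maximum taken from a profile without its peak can only equal the true Cmax or fall below it. A subject who leaves voluntarily just after the 0.50 h draw in Period 3 has given 3 of 28 samples (pre-dose, 0.25 h and 0.50 h). The last 25 are lost, and the 0.50 h value becomes Cmax. In R-T-R-T that subject has two reference values and so enters S_WR.

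The scaled limit in Step 2 is proportional to S_WR. One falsely low reference Cmax adds a large squared difference to S_WR² and makes the narrow-therapeutic-index criterion easier to meet. A falsely low test Cmax does the opposite: it shifts the ratio, inflates S_WT and can fail an acceptable product.

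**Working it through.** The plan states no within-subject SD, expected ratio, power or sample-loss rate, so there is no figure of its own to reproduce.

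**Inputs from the plan.** At least 48 completers out of about 64 dosed (7.1). θ = (ln(1/0.9)/0.10)² = 1.110, so √θ = 1.0536 (13.2.2, Step 2). Sampling every 15 minutes to 3.00 h, then 3.50 and 4.00 h (5.1.2.2). Median Tmax 1.5 h (7.6). Variability described only as small to medium (5.1).

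**Assumptions.** Within-subject SD 0.10, 0.15 or 0.20, equal for T and R; no subject-by-formulation variance; 24 subjects per sequence; one affected reference value reading a fraction f of the true Cmax.

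**1. How much loss it takes.** A two-compartment profile fitted to the label means in 3.3 (terminal share of AUC assumed 50 to 70%) gives:
- 1.50 h sample lost: f = 0.99 to 1.00
- 1.25 to 1.75 h (3 samples): 0.96 to 0.98
- 1.00 to 2.00 h (5 samples): 0.90 to 0.93
- 0.75 to 2.50 h (8 samples): 0.74 to 0.85
- 0.50 to 3.00 h (11 samples): 0.50 to 0.71

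A one-compartment sketch with Tmax 1.5 h gives 0.48 to 0.74 if sampling stops at 0.50 h.

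**2. Effect on S_WR.** From the Step 1 formula, one value shifted by d = ln f adds d²(1 − 1/n_i)/(2(n − 2)) to the expected S_WR². With n = 48 and n_i = 24 the divisor is 92.
- f = 0.50: 0.4805 × 0.9583/92 = 0.0050. At SD 0.10, S_WR = √0.0150 = 0.1225, and the implied limits exp(±1.0536 × S_WR) move from 90.0-111.1% to 87.9-113.8%.
- f = 0.75: 0.0828 × 0.9583/92 = 0.00086. S_WR = 0.1042, limits 89.6-111.6%.
- f = 0.90: S_WR = 0.1006, upper limit 111.18% against 111.11%.

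**3. False-pass rate.** Steps 1 and 2 were simulated as written (Howe bound, 40,000 runs per case), with the true ratio at the implied limit and one truncated Period 3 reference value. That subject has no second test value and so contributes no I_ij.

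| Assumed SD | Criterion | No truncation | f = 0.75 | f = 0.50 |
|---|---|---|---|---|
| 0.10 | scaled | about 5% | 8% | 34% |
| 0.15 | scaled | about 5% | 6% | 15% |
| 0.20 | all three in 13.4 | about 4% | about 4% | about 6% |

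With 64 subjects and f = 0.50, the scaled rates are about 30% (SD 0.10) and 13 to 14% (SD 0.15). For all three criteria, the 90% CI was taken from the sequence-adjusted I_ij contrast rather than PROC MIXED.

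**4. When the value also enters I_ij** (a completer with a gap; all criteria, f = 0.50). The low reference value raises the T/R estimate and widens its interval, so the two limits differ: 45% at the lower and 18% at the upper (SD 0.10); 21% and 9% (SD 0.15); 8.6% and 3.3% (SD 0.20). At f = 0.80 and SD 0.10 the lower limit gives 8.8%, and the upper stays at 5.3%.

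**5. Low test value.** SD 0.10, ratio 0.95, f = 0.50: the chance of passing falls from 92% to 80%.

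**6. After the fix.** With the affected Cmax set to missing, the false-pass rate at SD 0.10 returns to about 5%. Power at ratio 0.95 goes from 92.2% to 91.6%.

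**The case against.** The best defence is that the plan already screens such profiles. The second entry route in 13.1 is written for subjects with missed samples. If completers and two-period dropouts bypassed it, it would govern almost nobody, so it was probably meant more widely. Periods ended by an AE are removed, emesis within 3 hours leads to dismissal from the period (7.6), exclusions can be recorded before bioanalysis, and parameters are estimated only where possible. A period abandoned at 0.50 h is arguably an impacted one. Subjects are confined for 72 hours, so a non-AE departure before the peak is unlikely. Section 13.2.2 also defers detail to an SAP, and the combined document contains no separate SAP text in which to look for a Cmax rule.

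Much of this stands. A reader might infer that Cmax is kept whatever happens; the safeguards in 13.1 do not support that. A reader might also infer that any lost peak sample matters; the 15-minute grid makes one to five losses nearly harmless. Nor does every low reference value help the test product: once it enters I_ij, the gain is mainly at the lower limit.

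What remains is a gap in the stated rules. The routes are joined as alternatives. The reliability judgement has no criterion and precedes bioanalysis, so it cannot catch results found non-reportable later. The sentence restricting non-AE cases to non-impacted periods names dismissed subjects only, whereas the AE sentence names dismissed and withdrawn ones. Against that, the closing rule of 13.2.1 says affirmatively that Cmax "will be presented and included in the statistical analysis".

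**Conclusion.** The concern holds in a limited form. The plan can place a non-peak value into a primary endpoint, and its safeguards do not clearly stop this for completers, voluntary non-AE withdrawals after two completed periods, or results lost during bioanalysis. The event should be rare. A material effect needs sampling to stop before the peak, or roughly eight or more consecutive samples around it to be lost, in one reference period.

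If that happens, the false-pass rate of the scaled criterion rises from about 5% to between 8% and 34% at SD 0.10, and to between 6% and 15% at SD 0.15, for a value at 75% to 50% of peak. At SD 0.20 it stays near 4 to 6% for a dropout, because the 80-125% criterion takes over once S_WR passes about 0.21 (ln 1.25/1.0536 = 0.212). All SDs and fractions are assumptions.

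A reader might extrapolate to fractions well below 50% and conclude that one bad value nearly guarantees a pass. That would need almost the whole absorption and peak phase to be lost, and the documents give no loss rate to make it a working case.

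**What to change.** In 13.2.1, make the closing rule on missing last samples subject to a condition: a period's Cmax and Tmax enter Steps 1 to 4 only if reportable concentrations continue past the expected peak (for example to at least 3.00 h, the plan's own 2 × Tmax window in 7.6) and the observed maximum is followed by a lower reportable concentration. Otherwise set both to missing for that period and list them separately.

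For a gap inside an otherwise complete profile, set Cmax to missing only when most of the peak window is lost or the maximum lies next to the gap. Decide this without treatment codes, apply it also to results found non-reportable later, and report the Cmax results with and without flagged profiles. A bare count of consecutive losses would be a poor rule: a profile with its peak captured at 1.00 h but with 2.25 to 2.75 h missing would lose a valid Cmax.

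In 13.1, state that the reliability check applies per period to all three entry routes, and that the restriction to non-impacted periods also covers withdrawn subjects.

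The cost is a few sentences in 13.1, 13.2.1 and the SAP, and an occasional lost Cmax value.
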